1. LIST OF ABBREVIATIONS

The following abbreviations and specialist terms are used in this Statistical Analysis Plan.

Table 1: Abbreviations and Specialist Terms

Abbreviation	Definition
AE	adverse event
ADL	activities of daily living
AR(1)	Autoregressive (1)
ATC	anatomical therapeutic class
AUC _{inf}	area under the plasma concentration-time curve from time 0 to infinity
AUC _{0-t}	area under the plasma concentration-time curve from 0 to time t (last measurable concentration)
BLQ	below the limit of quantification
BMI	body mass index
C _{max}	maximum observed concentration
C-SSRS	Columbia-Suicide Severity Rating Scale
ECG	electrocardiogram
eCRF	electronic case report form
EOS	End-of-Study
EOT	end of treatment
ET	essential tremor
ETV	early termination visit
FAS	Full Analysis Set
ICF	informed consent form
IP	investigational product
MedDRA	Medical Dictionary for Regulatory Activities
MMRM	mixed effects model for repeated measures
PCS	potentially clinically significant

Abbreviation	Definition
[REDACTED]	[REDACTED]
PT	preferred term
[REDACTED]	[REDACTED]
QTcF	QT corrected according to Fridericia's formula
[REDACTED]	[REDACTED]
SAE	serious adverse event
SAP	statistical analysis plan
SOC	System Organ Class
$t_{1/2}$	terminal elimination half-life
TEAE	treatment-emergent adverse event
TETRAS	The Essential Tremor Rating Assessment Scale
T_{max}	time of occurrence of C_{max}
WHO-DD	World Health Organization Drug Dictionary

2. INTRODUCTION

This statistical analysis plan (SAP) is for the final analysis and is based on the approved clinical study protocol, Amendment 4, dated 15 December 2020, Version 5.

This SAP addresses the objectives of the study and describes the planned statistical analyses and data presentations, including the clinical pharmacology objective. All analyses and data presentations will be generated using SAS® Version 9.4 or higher Software (SAS Institute, Cary, North Carolina, USA). This SAP will be finalized and approved before the clinical database lock. Any changes made to the SAP after the clinical database lock has occurred will be documented and discussed in the clinical study report for this study.

3. STUDY OBJECTIVES

3.1. Primary Objective

The primary objective of this study is to assess the effect of SAGE-324 compared to placebo on upper limb tremor reduction in individuals with essential tremor (ET) after 28 days of treatment.

3.2. Secondary Objectives

The secondary objectives of this study are:

- To assess the effect of SAGE-324 compared to placebo on overall upper limb tremor reduction
- To assess the effect of SAGE-324 compared to placebo on activities of daily living (ADLs)
- To assess the effect of SAGE-324 compared to placebo on overall tremor
- To evaluate the safety and tolerability of SAGE-324

4. STUDY ENDPOINTS

4.1. Efficacy Endpoint

4.1.1. Primary Efficacy Endpoint and Estimand

The primary efficacy endpoint of this study is the change from baseline compared to placebo in The Essential Tremor Rating Assessment (TETRAS) performance subscale part 4 upper limb tremor score on Day 29.

[figure not shown]
The estimand for the primary efficacy endpoints is defined as follows:

[figure not shown]
1. *There are two treatment regiments for participants to be evaluated: SAGE-324 or placebo.*
2. *The target population consists of participants age 18-80 years inclusive, with diagnosis of essential tremor of at least 3 years duration.*
3. *The outcome for the primary efficacy endpoint is mean change from baseline in clinic-based TETRAS performance subscale part 4 upper limb tremor score at Day 29.*
4. *The population-level summary measure is the difference in mean change from baseline in clinic-based TETRAS performance subscale part 4 upper limb tremor score of between the two groups (SAGE-324 and placebo).*

4.1.2. Secondary Efficacy Endpoints

The secondary efficacy endpoints of this study are:

- Change from baseline compared to placebo in TETRAS performance subscale part 4 upper limb tremor score at all timepoints other than Day 29
- Change from baseline compared to placebo in Kinesia ONE accelerometer scores
- Change from baseline compared to placebo in the following:
 - TETRAS Scale ADL score
 - TETRAS Total Performance Score

[figure not shown]
[figure not shown]

4.2. Safety Endpoints

The safety endpoints of this study are:

- Incidence of treatment-emergent adverse events (TEAEs)

5. STUDY DESIGN

5.1. Overall Design

This is a randomized, double-blind, placebo-controlled, parallel group study to evaluate the efficacy, safety, and tolerability of SAGE-324 in individuals with ET. Participants, site staff, and sponsor personnel will be masked to treatment allocation.

This study includes a Screening Period of up to 28 days, a 29-day treatment period consisting of 28 days of dosing with the end of treatment visit intended to be on Day 29 at trough, and a 14-day follow-up period relative to final dose ([Figure 1](#)). After providing informed consent, participants will undergo screening assessments as outlined in [Appendix A](#) to determine eligibility.

[figure not shown]
The Screening Period begins with the signing of the informed consent form (ICF). Eligible participants will visit the study center on Day 1 and complete additional eligibility assessments of safety and efficacy as specified in the Schedule of Assessments ([Appendix A](#)). Following completion of screening and Day 1 eligibility checks, participants will be randomized to 1 of 2 treatment groups (SAGE-324 60 mg daily or placebo) in a 1:1 ratio.

During the double-blind Treatment Period, starting on Day 1, participants will receive a single dose of investigational product (IP) once daily in the morning with food for 28 days on an outpatient basis. Doses occurring on scheduled clinic visits will be administered in the clinic, and doses occurring on all other days will be self-administered by the participant at home as specified in [Appendix A](#). During the Treatment Period, participants will return to the study center approximately once per week for efficacy and safety assessments as specified in [Appendix A](#). In addition, a phone call will be conducted once per week, preferably midway between clinic visits, to review current status of the participant.

In addition to Kinesia ONE-specific training, clinical study center staff and study participants will be trained on the use of software applications and devices necessary to complete questionnaires or other assessments as required. During in-clinic visits, clinical study center staff will be available to assist participants as needed, to ensure they can access and use the software applications and devices correctly according to the training.

During the follow-up period, visits will be conducted on an outpatient basis. In addition to the phone calls to review current status, participants will receive a phone call approximately 7 days after the last dose of IP (ie, Day 35) for safety monitoring. Participants will return to the study center for an end of study visit approximately 14 days following the last dose of IP (ie, Day 42).

Figure 1: Study Design

Abbreviation: EOT = end of treatment

5.2. Sample Size and Power

The sample size of this study is based on the assumption of a 3 points difference in the change from baseline TETRAS performance subscale part 4 upper limb tremor score between SAGE-324 and placebo with a standard deviation of 3.5 points. Under these assumptions, a sample size of 25 evaluable participants per group would provide 85% power for detecting a placebo-adjusted treatment difference of 3 points in TETRAS performance subscale part 4 upper limb tremor score assuming a 2-sided test at an alpha level of 0.05. By including 2 treatment groups and using a 1:1 randomization, a total of 50 evaluable participants are required. Assuming a nonevaluability rate of 15%, approximately 60 participants will be randomized. Additional participants may be enrolled if the dropout rate is greater than 15%.

5.3. Randomization

This is a randomized, double-blind, placebo-controlled study. Participants will be randomized in a 1:1 ratio to treatment groups (SAGE-324, 60 mg daily or placebo). Participants, site staff, and the sponsor will be blinded to treatment allocation.

Randomization schedules will be generated by an independent statistician. The randomization schedules will be kept strictly confidential, accessible only to authorized personnel until the time of unblinding. The blinding of the study will be broken after the database has been locked.

5.4. Blinding and Unblinding

This is a randomized, double-blind, placebo-controlled study. Participants, site staff, and the sponsor will be blinded to treatment allocation. The randomization schedules will be kept strictly confidential, accessible only to authorized personnel until the time of unblinding after database lock.

[figure not shown]
During the study, the blind is to be broken only when the safety of a participant is at risk and the treatment plan is dependent on the study treatment received. Unless a participant is at immediate risk, the investigator should make diligent attempts to contact Sage prior to unblinding the study treatment administered to a participant. Requests from the investigator

about the treatment administered to study participants should be discussed with the Sage Medical Monitor. If the unblinding occurs without Sage's knowledge, the investigator must notify Sage within 24 hours of breaking the blind. All circumstances surrounding a premature unblinding must be clearly documented in the source records.

In all cases where the IP allocation for a participant is unblinded, pertinent information (including the reason for unblinding) must be documented in the participant's records and on the eCRF.

If a participant or any study personnel become unblinded to treatment, the participant will be excluded from the Per Protocol analysis set.

6. MODIFICATIONS

6.2. Modifications from the Approved Statistical Analysis Plan

This is the first version of the SAP for the final analysis.

6.3. Modifications from the Approved DMC Charter

Not applicable.

7. ANALYSIS SETS

7.1. All Participants Set

The All Participants Set will include all participants who have given written informed consent. This analysis set will be used for all listings and disposition.

7.2. Randomized Set

The Randomized Set will include all participants who are randomized.

7.3. Efficacy Analysis Set(s)

[figure not shown]
The Full Analysis Set will include all randomized participants who received any amount of IP and have a baseline and at least one postbaseline efficacy assessment.

The Per Protocol Set will include all participants in the Full Analysis Set without any major protocol deviations that could affect efficacy. The review of major protocol deviations will be completed, and the decision on whether the deviation affects efficacy will be documented before database unblinding. Note that a positive cotinine test on Days 1, 8, 15, 22, or 29 constitutes a major protocol deviation and excludes the participant from the Per Protocol Set. In addition, the Per Protocol Set will exclude full analysis set participants satisfying any of the following conditions:

1. Study Drug Adherence (defined in Section 8.2.7) < 75%
2. Inappropriate drug consumption (typically due to incorrect kit dispensation): if the participant consumed at any time during the study any study drug that the participant is not randomized to

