During the double-blind Treatment Period, starting on Day 1, participants will receive a single dose of investigational product (IP) once daily in the morning with food for 28 days on an outpatient basis (see Section 10.5). Doses occurring on scheduled clinic visits will be administered in the clinic, and doses occurring on all other days will be self-administered by the participant at home as specified in Table 2. During the Treatment Period, participants will return to the study center approximately once per week for efficacy and safety assessments as specified in Table 2. If on Day 1 or at any point during the treatment period, participants experience moderate or severe AEs of somnolence, drowsiness, dizziness or similar, or experience these events at any severity with associated symptoms such as confusion or balance impairment, they must have a dose interruption (drug holiday) of at least 1 day (missing at least 1 dose). Following a drug holiday, the dose of study drug must then be reduced by 15 mg decrements to tolerability (ie, from 60 mg to 45 mg to 30 mg). The dose of IP may not be increased for the remainder of the study. At the investigator's discretion, participants unable to tolerate the 30-mg dose will be discontinued from IP. During the study, a phone call will be conducted once per week, preferably midway between clinic visits, or more frequently if deemed appropriate by the investigator, to review the current status of the participant. Details regarding dose adjustment criteria and procedures are provided in Section 7.4.

In addition to Kinesia ONE-specific training, clinical study center staff and study participants will be trained on the use of software applications and devices necessary to complete questionnaires or other assessments as required. During in-clinic visits, clinical study center staff will be available to assist participants as needed, to ensure they can access and use the software applications and devices correctly according to the training.

During the follow-up period, visits will be conducted on an outpatient basis. In addition to the phone calls to review current status, participants will receive a phone call approximately 7 days after the last dose of IP (ie, Day 35) for safety monitoring. Participants will return to the study center for an end of study visit approximately 14 days following the last dose of IP (ie, Day 42).

Figure 1: Study Design

Abbreviation: EOT = end of treatment

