13.1. Data Analysis Sets

The Randomized Set will include all participants who are randomized.

The Safety Set will include all participants administered IP.

The Full Analysis Set will include all randomized participants who received any amount of IP and have a baseline and at least one postbaseline TETRAS performance subscale part 4 upper limb tremor score.

[REDACTED]

The Per Protocol Set will include all participants in the Full Analysis Set without any major protocol deviations that could affect efficacy. The review of major protocol deviations will be completed, and the decision on whether the deviation affects efficacy will be documented before database unblinding. Note that a positive cotinine test on Days 1, 8, 15, 22 or 29 constitutes a major protocol deviation.

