8.3.3. Analysis of Efficacy Variable(s)

The efficacy analysis uses the Full Analysis Set and presents data by randomized treatment, unless specified otherwise. The following efficacy endpoints will be summarized descriptively by randomized treatment at each scheduled time point:

- TETRAS performance subscale part 4 upper limb tremor scores (individual and total score by side and combined) – observed, change from baseline, percent change from baseline
- Kinesia ONE accelerometer scores – observed, change from baseline, percent change from baseline
- TETRAS performance total score – observed, change from baseline, percent change from baseline
- TETRAS ADL score - observed, change from baseline, percent change from baseline

The TETRAS performance subscale part 4 upper limb tremor change from baseline total score, TETRAS performance total score, TETRAS performance subscale Part 4/6/7/8 score, and TETRAS ADL score will also be presented by the following subgroups:

- Age group: <65, 65-80 years
- Sex: Male, Female
- Race: White, Black or African American, Other
- BMI (<18.5, 18.5-<25, 25-<30, ≥ 30 kg/m²)
- Age at essential tremor diagnoses (< 40 years, 40-60, >60 years)
- Age participant thinks essential tremor started (< 40 years, 40-60, >60 years)
- Years with essential tremor diagnosis (3-<6 years, 6-10 years, >10 years)
- Years since participant thinks essential tremor started (3-<6 years, 6-10 years, >10 years)
- Alcohol helps tremor: Yes (Intermediate, Worked Well), No (No, a little), NA
- Baseline TETRAS performance subscale part 4 upper limb tremor score (<12, ≥ 12)

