8.3.3.1.3. Sensitivity Analysis of Primary Endpoint

The following sensitivity analysis of the primary endpoint will be performed to assess the robustness of the primary analysis. For participants who terminate from treatment prior to the end of the analysis period for any of the following reasons: adverse event, noncompliance with study procedures, death, physician decision, or requires prohibited medication, missing measurements will be imputed as the worst post-baseline observation; for all other participants having missing measurements, missing values will be imputed with the last non-missing value before the scheduled visit time (LOCF principle).

If any of the sensitivity analyses yields a result that is in a different direction from the result of the primary analysis, the nature of the discrepancy will be examined to clearly explain the

discrepancy based on statistical principles and the discrepancy will be discussed in the clinical study report.

Another sensitivity analysis of primary endpoint will be performed to exclude the patients from the sites with potential risk of unblinding due to kit information accessed/downloaded, which is listed below:

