APPENDIX C. LIST OF DISPLAYS

Tables

14.1.1	Disposition of Participants (All Subjects)
14.1.2	Analysis Sets (All Subjects)
14.1.3.1	Major Protocol Deviations (Safety Set)
14.1.3.2	Protocol Deviations Related to Covid-19 (Safety Set)
14.1.4.1	Demographics and Baseline Characteristics (Safety Set)
14.1.4.2	Demographics and Baseline Characteristics - Subgroups (Safety Set)
14.1.5	Summary of Disease History (Safety Set)
14.1.6	Medical/Surgical History (Safety Set)
14.1.7.1	Prior Medications (Safety Set)
14.1.7.2	Concomitant Medications (Safety Set)
14.1.8.1	Study Drug Exposure (Safety Set)
14.1.8.2	Study Drug Adherence (Safety Set)
14.2.1.1	Summary of Essential Tremor Rating Assessment Scale (TETRAS) Performance Subscale Part 4 Upper Limb Tremor Score (Full Analysis Set)
14.2.1.2	Change from Baseline in the Essential Tremor Rating Assessment Scale (TETRAS) Performance Subscale Part 4 Upper Limb Tremor Score – Mixed Effect Model for Repeated Measures (MMRM) (Full Analysis Set)
14.2.1.3.1	Change from Baseline in the Essential Tremor Rating Assessment Scale (TETRAS) Performance Subscale Part 4 Upper Limb Tremor Score – Sensitivity Analysis – Missing Data Imputation (Full Analysis Set)
14.2.1.3.2	Change from Baseline in the Essential Tremor Rating Scale (TETRAS) Assessment Performance Subscale Part 4 Upper Limb Tremor Score – Sensitivity Analysis – Excluding Subjects From Sites 001, 002, 003, 004, 007, 008, 010, 011, 017, 019, 021, 023, 024 (Full Analysis Set)
14.2.1.4	Summary of Essential Tremor Rating Assessment Scale (TETRAS) Performance Subscale Part 4 Upper Limb Tremor Score (Per Protocol Set)
14.2.1.5	Change from Baseline in the Essential Tremor Rating Assessment Scale (TETRAS) Performance Subscale Part 4 Upper Limb Tremor Score – Mixed Effect Model for Repeated Measures (MMRM) (Per Protocol Set)
14.2.1.6	Summary of Essential Tremor Rating Assessment Scale (TETRAS) Performance Subscale Part 4 Upper Limb Tremor Score by Subgroup, Total Score (Full Analysis Set)
14.2.1.7	Change from Baseline in the Essential Tremor Rating Assessment Scale (TETRAS) Performance Subscale Part 4 Upper Limb Tremor Score by Subgroup, Total Score - Mixed Effect Model for Repeated Measures (MMRM) (Full Analysis Set)
14.2.2.1	Summary of Essential Tremor Rating Assessment Scale (TETRAS) ADL (Full Analysis Set)

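### The missing-data sensitivity analysis of the primary endpoint cannot count dosed participants who were never rated after baseline

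*SAP*

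**What the plan says.** SAP 7.3 defines the Full Analysis Set (FAS) as "all randomized participants who received any amount of IP and have a baseline and at least one postbaseline efficacy assessment". Protocol Amendment 4, 13.1, has the same structure but ties entry to the primary scale: participants must "have a baseline and at least one postbaseline TETRAS performance subscale part 4 upper limb tremor score". The SAP thus accepts any efficacy measure, while the protocol requires the TETRAS part 4 score.

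SAP 8.3.3 makes this set the default: "The efficacy analysis uses the Full Analysis Set and presents data by randomized treatment, unless specified otherwise". Appendix C labels the primary MMRM, the two sensitivity analyses and the subgroup analyses with the FAS. The title of Table 14.2.1.3.1 ends "Missing Data Imputation (Full Analysis Set". The supportive analyses use the Per Protocol Set, which is a subset of the FAS. The Randomized Set is defined in 7.2, but no visible efficacy display uses it.

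SAP 8.3.3.1.3 gives two imputation rules. For participants who stop treatment for listed reasons, adverse events among them, "missing measurements will be imputed as the worst post-baseline observation". For everyone else, "missing values will be imputed with the last non-missing value before the scheduled visit time (LOCF principle".

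**The concern.** Having a postbaseline rating is something that happens after randomisation, and treatment can affect it. The first scheduled rating is Day 8. The protocol classes somnolence as an adverse drug reaction (5.2) and plans for sedation from the first dose: "If on Day 1 or at any point during the treatment period, participants experience moderate or severe AEs of somnolence".

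The primary MMRM models postbaseline change, so a participant with no postbaseline value adds nothing to it whichever set is named. The sensitivity analysis is where such a person could be counted, and there the treatment of dropouts is uneven. Someone who stops for an adverse event after a Day 8 rating has later visits filled with their worst value. Someone who leaves for the same reason on Day 5 and is never rated again is not in the table. If such losses fell mainly on SAGE-324, the one analysis meant to penalise stopping for intolerance would miss its earliest cases.

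**Working it through.** **1. The plan's own figures.** SAP 5.2 assumes a 3-point difference, SD 3.5, two-sided alpha 0.05 and 25 evaluable per group, and states 85% power. The normal approximation gives 85.8% and the noncentral t gives 84.4%, so the figure reproduces. Inflating for 15% nonevaluable, 50 / 0.85 = 58.8, or 59, against about 60 stated. No stated number is wrong. These figures only supply the scale for step 4.

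**2. Who is lost.**
- A participant who stops drug early is encouraged to attend the end-of-treatment (EOT) visit and later the end-of-study/early-termination (EOS/ETV) visit (Protocol 8.4.1). TETRAS is scheduled at both.
- SAP 8.3.2 maps EOT and early-termination ratings to analysis windows. The first window runs from after the Day 1 dose to Day 11, so an early EOT rating becomes a Day 8 record.
- A participant therefore falls outside the FAS only with no Day 8, EOT or EOS/ETV rating and no other postbaseline one.

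**3. What the imputation rules do for them.**
- The worst-postbaseline rule needs at least one postbaseline value, so it is undefined here. Widening the population without adding a rule would not be enough.
- The carry-forward rule, read literally, could take the baseline value, but the SAP does not say so.
- The wording mismatch creates a related case. A participant with, say, a postbaseline Kinesia score but no part 4 score is inside the SAP's FAS and outside the protocol's. For that person the worst-value rule fails within the analysed set.

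**4. Illustrative size.** The documents give neither the number nor the arm of never-rated participants. Assume 30 dosed per arm, k never-rated participants all on SAGE-324, a true difference of 3 points among the rest, a mean placebo improvement of m points, and zero change for the k. Then

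all-dosed difference = (3 + m)(1 − k/30) − m.

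With m = 0, zero change is the same as no benefit over placebo. For k = 3: 3 × 27/30 = 2.70 at m = 0; 4 × 0.9 − 1 = 2.60 at m = 1; 5 × 0.9 − 2 = 2.50 at m = 2.

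The power columns use a two-sample noncentral t at m = 0. The all-dosed column widens the SAGE-324 variance for the mixture: at k = 3 it is 3.5² + 0.1 × 0.9 × 9 = 13.06, giving a pooled SD of √((13.06 + 12.25)/2) = 3.56.

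| k | All-dosed difference, m = 0 | m = 2 | Difference with the k dropped | Power, k dropped | Power, all dosed |
|---|---|---|---|---|---|
| 1 | 2.90 | 2.83 | 3.0 | 90% | 88% |
| 2 | 2.80 | 2.67 | 3.0 | 89% | 85% |
| 3 | 2.70 | 2.50 | 3.0 | 89% | 82% |
| 4 | 2.60 | 2.33 | 3.0 | 88% | 79% |

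For scale, the standard error of the difference with 30 per arm is 3.5 × √(2/30) = 0.90.

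**The case against.** The strongest reply is that very few people can fall through. EOT and EOS/ETV visits catch most early stoppers. The sedation rule describes how participants continue: Protocol 7.1 and 7.4 require an interruption and then a lower dose, and stopping the drug becomes mandatory only if events persist or recur after a second round. The one explicit rule that ends TETRAS assessments is a positive alcohol test (9.2.3), which is not a drug effect. This stands. A reader might infer from the sedation text that SAGE-324 will lose more participants before any rating. That is possible, because attendance is only encouraged and withdrawal is free, but the documents do not show it.

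The SAP is also not silent on these people. Section 8.2.1 summarises the size of each analysis set by randomised arm, gives reasons for stopping treatment and study, and lists exclusions from each set (Tables 14.1.1 and 14.1.2, Listing 16.2.3). Comparing Safety Set and FAS counts will show how many were dosed and left out. This stands too, and reduces what has to be added.

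Finally, the illustration is mostly assumption. It puts every loss in one arm. At k = 4 it uses most of the 4.5 participants per arm (15% of 30) that the plan allows as nonevaluable. One or two losses move the difference by 0.1 to 0.2 at m = 0, well under one standard error. The larger figures at m = 2 arise because zero change makes the leavers worse than placebo. All of this is correct. It limits the size, but it does not supply the missing rule in 8.3.3.1.3.

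**Conclusion.** The point holds in a limited form. In the visible SAP, dosed participants with no postbaseline efficacy assessment are outside the FAS. The missing-data sensitivity analysis is run on that set, and its rule for adverse-event dropouts is undefined for them. The analysis therefore cannot address the earliest dropouts. On the assumptions shown, each uncounted SAGE-324 participant corresponds to about 0.1 point, and three to 0.3 point (2.7 against 3.0). The gap is larger only if placebo improves and leavers are given zero change. If nobody is lost unrated, the effect is nil.

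Two stronger readings go beyond the documents. A reader might conclude that no efficacy analysis anywhere counts these participants, but parts of the SAP's efficacy section are redacted, so this can be said only of what is visible. A reader might also conclude that the FAS estimate is inflated by a known amount. The number, arm and true outcome of the never-rated participants are all unknown, so neither the direction nor the size of any bias is established.

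The change is still worth making before unblinding. It is cheap, and without it no visible analysis would show the effect of such losses.

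**What to change.** In SAP 8.3.3.1.3 and Table 14.2.1.3.1, define the population of the missing-data sensitivity analysis as all randomised participants who took any study drug and have a baseline part 4 score. State that those with no postbaseline part 4 score have baseline carried forward, that is, zero change at each postbaseline visit in the model. This extends the SAP's existing carry-forward rule to people whose last value is baseline. Keep the present rules for everyone else.

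Replace the SAP 7.3 entry condition with the protocol's part 4 score requirement, so that the two documents define one FAS.

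The by-arm counts are already planned. Add only the reasons for participants who were dosed but are not in the FAS.

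The primary MMRM stays as it is. The cost is one SAP paragraph, one changed table population and one aligned definition. The drawback is a single-value assumption for what should be a few participants, confined to a sensitivity analysis.
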